8.2.4.2 Physical Examinations

Complete physical examinations will be performed as outlined in [Appendix A](#). Complete physical examinations will include a minimum of a review of the patient's general appearance, head, eyes, ears, nose, and throat (HEENT), neck, heart, lungs, abdomen, back and extremities, skin, and general neurological system.

Symptom-oriented physical examinations will be performed at all other time points and as clinically indicated.

In addition, weight will be captured during each physical examination. Efforts should be made to standardize weight collection across all patients and visits. Patients should be instructed to remove shoes and heavy clothing (eg, heavy coats, jackets) prior to measurement. For weight collection, an effort should be made to use the same scale throughout the study where possible. In instances where multiple scales may be used, efforts should be made to reset the scale to zero prior to collection of weight measurement.

8.2.4.3 Electrocardiograms

Electrocardiograms (12-lead ECGs) will be performed as specified in [Appendix A](#).

8.2.4.4 Adverse Events of Special Interest

Monitoring of these events will be the responsibility of the DSMB. The process of data collection and assessment of the events will be detailed in a separate DSMB charter.

Additional information will be collected if episodes of any of the following AEs of special interest occur.

8.2.4.4.1 Central Nervous System Events

Central nervous system events of special interest may include any clinically significant changes in mood, physical affect, or exacerbation of preexisting CNS conditions (eg, depression, migraine headaches).

8.2.4.4.1.1 Depression Detection

Patients will be evaluated beginning at Day 1 (Baseline) and at each subsequent visit for indications of depression. During each visit the patient will first be asked to respond to the question “During the past month, have you often been bothered by feeling down, depressed, or hopeless?” Followed by “During the past month, have you often been bothered by little interest or pleasure in doing things?” A positive response prior to Day 1 dosing will be captured on the medical history CRF page. Positive responses following the first dose will be captured as an AE and will be followed as an AE of special interest.

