9.1 Adverse Events

It is the responsibility of the Investigator to document all AEs that occur during the study.

Adverse event is defined as any untoward medical occurrence associated with the use of a drug in humans, whether or not considered drug related.

Life-threatening adverse event or life-threatening suspected adverse reaction: An adverse event or suspected adverse reaction is considered "life-threatening" if, in the view of either the Investigator or Sponsor, its occurrence places the patient or subject at immediate risk of death. It does not include an adverse event or suspected adverse reaction that, had it occurred in a more severe form, might have caused death.

An AE includes any noxious, pathological, or unintended change in anatomical, physiological, or metabolic functions as indicated by physical signs or symptoms occurring in any phase of the clinical study whether or not considered related to the study medication.

This definition includes an exacerbation of preexisting medical conditions or events, historical condition not present prior to study treatment, which reappear following study treatment, intercurrent illnesses, hypersensitivity reactions, drug interaction, or the significant

worsening of the disease under investigation that is not recorded elsewhere in the CRF.

Anticipated day-to-day fluctuations of pre-existing conditions that do not represent a clinically significant exacerbation or worsening need not be considered AEs.

Any laboratory abnormality fulfilling the criteria for a SAE ([Section 9.2](#)) should be reported as such, in addition to being recorded as an AE. Any treatment-emergent abnormal laboratory result which is clinically significant, ie, meeting 1 or more of the following conditions, should be recorded as a single diagnosis AE:

- Is considered to be an SAE,
- Results in discontinuation from study treatment, or
- Results in a requirement for a change in concomitant therapy (ie, addition of concomitant therapy)

In the event of medically significant unexplained abnormal laboratory test values, the tests should be repeated and followed up until they have returned to the normal range and/or an adequate explanation of the abnormality is determined.

TEAEs are defined as any AEs reported after the first dose of study drug on Day 1. Adverse events reported after consent of a patient, but before administration of study medication, will be reported in the Medical History.

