10.4.2.1 Adverse Events

All AEs will be coded and listed by body system and preferred term based on the Medical Dictionary for Regulatory Activities (MedDRA). Summaries using descriptive statistics will be provided for treatment-emergent AEs, drug-related AEs and AEs by intensity. Treatment-emergent AEs are those events not present at Baseline, but occurring after the start of study drug, or if existing at Baseline, increasing in intensity after initiation study drug. Summaries made by intensity will select the event with the highest intensity when multiple occurrences of the same event are reported for the same patient. In a similar manner, summaries prepared by drug relationship will select the event with the greatest degree of relationship when a study reports multiple occurrences of the same event. On-study deaths will be reported for deaths occurring during the active phase of the treatment period and 30 days after stopping study drug. Also, deaths occurring outside the 30-day window, but secondary to an AE reported within the 30-day post treatment period, will be reported as well.

Listings will be provided for deaths, SAEs, and discontinuations due to AEs. Additional summaries or listings of AEs may also be provided.

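### In Amendments 2 and 3, every positive depression screen after the first dose becomes an AE of special interest without comparison with the patient's Day 1 answer, so an unchanged Day 1 positive is recorded as an on-treatment event

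*Protocol*

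**What the plan says.** The point concerns the full text of Amendment 3 (Germany and UK sites). Amendment 2 carries the same depression rule.

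- Section 8.2.4.4.1.1, screening: "Patients will be evaluated beginning at Day 1 (Baseline) and at each subsequent visit for indications of depression". There are two questions about the past month, and the rule turns only on whether the response is positive.
- Section 8.2.4.4.1.1, before the first dose: "A positive response prior to Day 1 dosing will be captured on the medical history CRF page".
- Section 8.2.4.4.1.1, after the first dose: "Positive responses following the first dose will be captured as an AE and will be followed as an AE of special interest".
- Section 8.2.4.4.1 says that CNS events of special interest may include "any clinically significant changes in mood, physical affect, or exacerbation of preexisting CNS conditions".
- Section 8.2.4.4 makes the DSMB responsible for monitoring these events and leaves the process to a separate charter. Section 5.1 has the DSMB review safety data quarterly.
- Section 9.1, on what is an AE: "Anticipated day-to-day fluctuations of pre-existing conditions that do not represent a clinically significant exacerbation or worsening need not be considered AEs".
- Section 9.1, on treatment emergence: "TEAEs are defined as any AEs reported after the first dose of study drug on Day 1".
- Section 10.4.2.1 instead describes treatment-emergent AEs as "those events not present at Baseline, but occurring after the start of study drug, or if existing at Baseline, increasing in intensity" after starting study drug.

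Amendment 4 changes Section 8.2.4.4.1.1. The investigator first judges whether a post-dose positive answer is an AE, and only then is it followed as one of special interest. Amendment 4 is marked as applying to North America only, so the documents do not show the rule replaced elsewhere.

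**The concern.** The rule uses the Day 1 answer for one purpose, an entry in medical history, and then ignores it. Someone who answers yes on Day 1 and gives the same yes at Week 12 must be entered as an AE and followed as one of special interest, although the screen shows no change. The Amendment 3 and Amendment 2 rule also has no step at which the investigator could decide that nothing has happened.

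Long-term safety is the primary objective, CNS events are the only events of special interest that Section 8.2.4.4 lists, and the study has no control arm from which to judge background depression. The patient's own Day 1 status is the main reference available. If it is not carried through, the special-interest set mixes new low mood with low mood already present at entry, and its frequency cannot be read as either.

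**Working it through.** The plan states no figure on this point, so there is nothing to reproduce. The check compares the passages for one patient and then gives an illustration of size.

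**Step 1. Follow one patient: positive on Day 1, positive and unchanged at Week 12.**

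- Section 8.2.4.4.1.1: medical history on Day 1; AE and AE of special interest at Week 12.
- Section 9.1, AE definition: an unchanged pre-existing condition need not be an AE. The site is thus told both that it must record the answer and that it need not.
- Section 9.1, TEAE definition: once recorded as an AE after the first dose, it is treatment-emergent.
- Section 10.4.2.1, TEAE definition: present at Baseline and not increased in intensity, so not treatment-emergent.
- Special-interest set: included, with no Baseline condition attached.

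The same patient is in or out of the TEAE tables according to which section the programmer follows, and is in the special-interest set either way.

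**Step 2. Opportunities.** The Amendment 3 schedule has screens at Weeks 12, 24, 36, 48, 60, 72 and 84 (7), optional Weeks 96 and 108 (2) and follow-up (1): 7 + 2 + 1 = up to 10 post-dose screens. One positive is enough.

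**Step 3. Size, by assumption.** Let p be the share positive on Day 1 and r the share of those positive again at any later screen, with nothing worsened. Neither is in the documents.

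Excess patients per 100 = 100 × p × r

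- p = 0.10: r = 0.5 gives 5; r = 1.0 gives 10
- p = 0.20: r = 0.5 gives 10; r = 1.0 gives 20
- p = 0.30: r = 0.5 gives 15; r = 1.0 gives 30

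If 10% of Day 1-negative patients also had a new positive (a further assumption), the total under the rule is 100 × [p × r + (1 − p) × 0.10]. This runs from 100 × (0.05 + 0.09) = 14 to 100 × (0.30 + 0.07) = 37. Leaving out unchanged Day 1 positives, it is 100 × (1 − p) × 0.10 = 7 to 9.

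**Step 4. How firm is r?** If a Day 1-positive patient says yes at each visit with probability q, independently, the chance of at least one yes in the 7 visits through Week 84 is 1 − (1 − q)^7: 0.918 at q = 0.3 and 0.992 at q = 0.5. Mood answers from one patient are unlikely to be independent. With a beta-binomial of the same means and within-patient correlation 0.5, the chance falls to 58% and 79%. Step 3 therefore uses a wide range for r and no visit model.

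**The case against.** The strongest reply is that recording is not counting. Section 8.2.4.4.1.1 says what goes on the CRF, and Section 10.4.2.1 supplies the Baseline comparison for the summaries. That is correct for TEAE tables built on 10.4.2.1. A reader might infer that every TEAE table is inflated; the documents do not support that. What remains is the competing definition in 9.1, and the special-interest set, to which neither definition is applied.

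Other points against, and what stands of each:

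- The special-interest paragraph says what such events may include. It is not a closed definition, so a wider trigger does not strictly contradict it. This stands; the conflict is with 9.1 and 10.4.2.1.
- A reader might infer that a yes/no screen makes a judgement of worsening impossible. Section 9.1 has the investigator grade each AE as mild, moderate or severe, so a post-dose grade exists. Whether a Day 1 grade exists is not stated.
- The DSMB may look at these events against Day 1. Its charter is not in the documents, so harm to its review is possible but not shown.
- Sections 10.4.2 and 10.4.2.1 name no incidence table for events of special interest, so no specified table can be said to be wrong by a given amount.
- Day 1 is not drug-free: Phase 3 patients enter at Week 48 without interruption of study drug. This stands and limits what a Day 1 comparison can show.
- Broad capture is a defensible choice in a single-arm safety study. It is compatible with a split by Day 1 status, which keeps every report.

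**Conclusion.** The point holds for Amendment 3 and Amendment 2. The recording rule turns an unchanged Day 1 positive into an on-treatment AE of special interest. It conflicts with the AE definition in 9.1, and only one of the two TEAE definitions removes the case afterwards. Amendment 4 adds an investigator judgement but does not explicitly call for comparison with Day 1.

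The direction of the effect follows from the text; its size does not. About 5-30 extra patients per 100 rests wholly on an assumed 10-30% positive on Day 1 and 50-100% of those positive again. It is a rate: Amendment 3 expects up to 100 patients in the whole study, and the share under each amendment is not given.

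A reader might infer that nearly every Day 1-positive patient will trip the rule, or that the depression rate mostly reproduces prevalence at entry. Neither is supported. The first needs independence between visits. The second fails under equally arbitrary inputs: if Day 1-negative patients say yes with probability 0.05 per visit, 1 − 0.95^7 = 30% do so at least once in 7 visits. At 20% Day 1 prevalence they contribute 0.8 × 30% = 24 points, against 18-20 points (0.2 × 0.918 to 0.2 × 0.992) from Day 1-positive patients.

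**What to change.** 1. Reconcile Section 8.2.4.4.1.1 with Sections 9.1 and 10.4.2.1 in the amendments that carry the unconditional rule, so that a post-dose positive answer is assessed against the patient's Day 1 answer before it is classed as an AE of special interest. Amendment 4's investigator assessment is a starting point; the reference to Day 1 should be made explicit there too.
2. Settle on one TEAE definition across 9.1 and 10.4.2.1.
3. Tabulate depression events of special interest separately for Day 1-negative and Day 1-positive patients. Keep all reports visible, and read only the Day 1-negative group as new onset during this study. This also works for data already collected, because positive Day 1 answers are on the medical history page.

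The cost is a short text change, one extra table split and an investigator judgement for Day 1-positive patients. The limitation should be stated with the table: Day 1 follows earlier exposure in the lead-in studies, so the Day 1-negative rate does not capture depression that arose before entry.

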8.3 Other Assessments

8.3.1 Chromogranin A (CgA)

Blood samples for measurement of chromogranin A (CgA) levels will be collected as indicated in [Appendix A](#).

8.3.2 Disease Progression

Data will also be collected on measures of disease progression as performed as standard of care including, but not limited to: interpretation of clinical scans (eg, PET, CAT, MRI scans of tumor), or Investigator assessment of disease status, while the patient is enrolled in the study.

8.3.3 Quality of Sleep Assessment

Quality of sleep will also be evaluated beginning Day 1 (Baseline) and at each subsequent visit thereafter. Patients will be asked to respond to the following question “Since your last visit, how many times a night (on average) do you wake up due to your CS symptoms?” based on the following scale 0, 1, 2, 3, 4, >4.

8.4 Appropriateness of Assessments

The assessments used in this study conform to the usual clinical and laboratory assessments of patients with CS participating in clinical trials and are typical of a Phase 3 study.

9.1 Adverse Events

It is the responsibility of the Investigator to document all AEs that occur during the study.

Adverse event is defined as any untoward medical occurrence associated with the use of a drug in humans, whether or not considered drug related.

Life-threatening adverse event or life-threatening suspected adverse reaction: An adverse event or suspected adverse reaction is considered "life-threatening" if, in the view of either the Investigator or Sponsor, its occurrence places the patient or subject at immediate risk of death. It does not include an adverse event or suspected adverse reaction that, had it occurred in a more severe form, might have caused death.

An AE includes any noxious, pathological, or unintended change in anatomical, physiological, or metabolic functions as indicated by physical signs or symptoms occurring in any phase of the clinical study whether or not considered related to the study medication.

This definition includes an exacerbation of preexisting medical conditions or events, historical condition not present prior to study treatment, which reappear following study treatment, intercurrent illnesses, hypersensitivity reactions, drug interaction, or the significant

worsening of the disease under investigation that is not recorded elsewhere in the CRF.

Anticipated day-to-day fluctuations of pre-existing conditions that do not represent a clinically significant exacerbation or worsening need not be considered AEs.

Any laboratory abnormality fulfilling the criteria for a SAE ([Section 9.2](#)) should be reported as such, in addition to being recorded as an AE. Any treatment-emergent abnormal laboratory result which is clinically significant, ie, meeting 1 or more of the following conditions, should be recorded as a single diagnosis AE:

- Is considered to be an SAE,
- Results in discontinuation from study treatment, or
- Results in a requirement for a change in concomitant therapy (ie, addition of concomitant therapy)

In the event of medically significant unexplained abnormal laboratory test values, the tests should be repeated and followed up until they have returned to the normal range and/or an adequate explanation of the abnormality is determined.

TEAEs are defined as any AEs reported after the first dose of study drug on Day 1. Adverse events reported after consent of a patient, but before administration of study medication, will be reported in the Medical History.

AEs should not be solicited with leading questions that suggest specific signs or symptoms. Rather, AEs should be solicited by asking the patient a non-leading question such as: “Do you feel different in any way since receiving the dose or since the last assessment?”

The Investigator will evaluate all AEs with regard to the maximum intensity and relationship to study drug, as follows:

- Maximum intensity

Maximum intensity should be assigned using 1 of the following 3 severity grades:

- Mild: aware of event but easily tolerated
- Moderate: discomfort, enough to cause interference with usual activity
- Severe: incapacitating: patient unable to work or perform usual activities

- Relationship to study drug

Not related:

- Does not follow a reasonable temporal sequence from administration of the drug

- Could be reasonably explained by other factors, including underlying disease, complications, concomitant drugs, or concurrent treatment.

Possibly related:

- That follows a reasonable temporal sequence from administration of the drug (including the course after withdrawal of the drug), or
- For which the possibility of the study drug being the causative factor (eg, existence of similar reports attributed to the suspected drug and its analogues; reactions attributable to the pharmacological effect) could not be excluded, although other factors such as underlying disease, complications, concomitant drugs, or concurrent treatment are presumable.

Probably related:

- That follows a reasonable temporal sequence from administration of the drug (including the course after withdrawal of the drug), and
- For which the possibility of factors other than the drug, such as underlying disease, complications, concomitant drugs, or concurrent treatment, could not be excluded as the cause.

Definitely related:

- Follows a clear temporal sequence from administration of the study drug.
- Could not be possibly explained by the known characteristics of the patient's clinical state, environmental or toxic factors, or other modes of therapy administered to the patient.
- Disappears or decreases on cessation or reduction in dose of the study drug.
- Reappears or worsens when the study drug is re-administered.
- Follows a response pattern known to be associated with administration of the study drug.

The degree of certainty with which an AE is attributed to treatment with study medication (or alternative causes, eg, natural history of the underlying diseases, concomitant therapy, etc.) will be determined by how well the event can be understood in terms of known pharmacology of the study medication and/or reaction of similar nature being previously observed with the study medication or the class of study medication.

All AEs should be followed for at least 30 days following the last dose of study drug or until the event has resolved, the condition has stabilized, or the patient is lost to Follow-up. For

each patient for whom an AE was reported that did not resolve before the end of the reporting period, Follow-up information on the subsequent course of events must be submitted to the Sponsor. This requirement indicates that follow-up may be required for some AEs after the patient has completed his/her participation in the study

9.2 Serious Adverse Events (SAEs)

An SAE is defined as any event that results in any of the following outcomes:

1. Death
2. A life-threatening adverse event;
3. Inpatient hospitalization or prolonging of an existing hospitalization (see [Section 9.2.1](#) for information on hospitalization as an SAE);
4. A persistent or significant incapacity or substantial disruption of the ability to conduct normal life functions; or
5. A congenital anomaly/birth defect.

Important medical events that may not result in death, be life-threatening, or require hospitalization may be considered serious when, based upon appropriate medical judgment, they may jeopardize the subject and may require medical or surgical intervention to prevent one of the outcomes listed above.

Any SAE must be reported by telephone or facsimile within 24 hours of discovery of the event. Investigators should not wait to receive additional information to fully document the event before notifying the Sponsor of an SAE at:

Sites in North America must report to:

Safety Data [contact]
Safety [contact]

Email address (in case of fax failure): [contact]

Sites outside North America must report to the country specific toll-free fax numbers identified below:

Australia: [REDACTED]
Belgium: [REDACTED]
Brazil: [REDACTED]
France: [REDACTED]
Germany: [REDACTED]
Israel: [REDACTED]
Italy: [REDACTED]
Netherlands: [REDACTED]

Spain: [REDACTED]
Sweden: [REDACTED]
United Kingdom: [REDACTED]

Email Address (in case of fax failure): [REDACTED]

The telephone report should be followed by full written summary detailing relevant aspects of the SAE in question using the provided SAE report form. Where applicable, information from relevant hospital case records and autopsy reports should be obtained. The SAE should also be recorded on the AE page of the patient's CRF.

An SAE that occurs after completion of the study but, in the opinion of the Investigator, is related to the study medication, should be reported as described for an SAE. If an AE does not meet the regulatory definition of "serious" but is considered by the Investigator to be related to the study medication and of such clinical concern as to influence the overall assessment of safety, it must be reported as defined for an SAE.

All patients (including discontinued patients) with a SAE must be followed until the event resolves or reaches a new Baseline, but for a minimum of 30 days after the last dose of study drug.

